10 CHANGES TO TRIAL CONDUCT

10.1 Protocol Amendments

Before implementation of substantial changes (as defined in EU guidance documents [[European Commission 2006, 2010](#)]) unless considered an Urgent Safety Measure, approval/favourable opinion must be obtained from the appropriate regulatory authority(ies) and IEC(s).

10.2 Premature Termination of the Trial

In case of premature termination of the trial, health authorities, and IECs will be notified in writing, including the reason for premature termination.

Conditions that may warrant premature termination of the trial include, but are not limited to the following:

- The discovery of an unexpected and significant or unacceptable risk to the subjects enrolled in the trial
- A decision of the Sponsor to discontinue development of the drug

10.3 Premature Termination of a Trial Site

The Sponsor can decide to prematurely terminate a site. Conditions that may warrant termination include, but are not limited to:

- Insufficient adherence to protocol requirements
- Failure to enrol subjects at an acceptable rate

Clinical Trial Protocol

11 DATA HANDLING AND RECORD KEEPING

11.1 Data from Clinical Trial Sites

Data from clinical trial sites will be entered in an eCRF.

The investigator will sign relevant eCRF sections by use of an electronic signature. Only the investigator (i.e. medically qualified personnel) can sign data on medical assessments. Any corrections made by the investigator or authorised staff to the eCRF after original entry will be documented in an audit trail. The person making the change and the date, time and reason for the change will be identified in the audit trail. Changes to the data already approved/signed by an investigator will require re-signature by the investigator. The investigator (principal investigator or sub-investigator) will sign all patient data in the eCRF by an electronic signature.

Subject data will be recorded anonymously and the subjects will be identified only by a screening number.

The monitor will check the eCRF for accuracy and completion and perform source data verification. Data entered in the eCRF will be verified against source data. The level of source data verification is described in Section 11.2.

11.2 Source Data

All data entered in the eCRF should be verifiable by source data in the subject's medical record or other records at the trial site, as applicable:

- Details of the trial (trial ID and subject screening and enrollment number)
- Date(s) of informed consent of the subject
- Data of each trial visit including signature and /or initials of person(s) conducting the visit
- Data and information of any relevant telephone contact with the subject and signature and/or initials of person(s) conducting or receiving the call
- Subject's date of birth
- Diagnosis of IPF including start date, HRCT date and report/image
- Medical history and concomitant illness including start and stop dates
- Concomitant medication including start and stop dates
- Overall conclusion of the subject's eligibility
- Conclusion and results for each in-/exclusion criterion with respect to fulfillment of trial eligibility or not
- Physical examination
- Slit lamp data
- Height and body weight
- Blood pressure, pulse, body temperature and ECG

Clinical Trial Protocol

Vicore Pharma AB
Trial ID: VP-C21-005

Version: 7.0
Date: 15-Sep-2021

- All laboratory samplings and data, including date and time of blood sampling (including subjects in PK subset)
- Investigator's evaluation of haematology and biochemistry results being out of range
- Date and times of blood sampling
- Spirometry data
- All AEs, SAEs and pregnancies described in details
- IMP dispensed and date of dispensing, IMP retrieval and date of retrieval
- Premature withdrawal of subject from the trial including reason and withdrawal criteria fulfilled
- Investigator treatment evaluations

11.3 Coding of Data

Medical history and AEs will be coded using the latest version of Medical Dictionary for Regulatory Activities (MedDRA).

Concomitant medication will be coded using the latest version of World Health Organisation (WHO) Drug Reference List.

11.4 Subject Confidentiality

The confidentiality of the subject data and subject records shall be protected, respecting the privacy and confidentiality rules in accordance with applicable regulatory requirements.

12 RETENTION OF DOCUMENTS

The monitor will instruct the investigator to maintain source documents and the signed informed consent form for each subject.

Furthermore, the monitor will instruct the investigator to archive essential documents for the duration defined in the ICH Guideline E6 (Note for Guidance on Good Clinical Practice [ICH 1997]) or for 15 years, whichever comes first.

The duration of archiving defined in the ICH Guideline E6 is as follows:

Essential documents should be retained until at least 2 years after the last approval of a marketing application in an ICH region and until there are no pending or contemplated marketing applications in an ICH region or at least 2 years have elapsed since the formal discontinuation of clinical development of the investigational product. These documents should be retained for a longer period however if required by the applicable regulatory requirements or by an agreement with the Sponsor.

The Sponsor will notify the investigator when retention of the trial-related records is no longer required.

Clinical Trial Protocol

13 STATISTICAL METHODS

The principal features of the statistical analysis to be performed are described in this section. A more technical and detailed elaboration of the principal features will be presented in a separate statistical analysis plan, which will be signed and approved prior to the database lock.

13.1 Sample Size and Power Considerations

Sample size is based on assumptions of a 40 mL decline in FVC/24 weeks and a standard deviation of 200 mL. With 55 evaluable subjects there is a 90% power that the 90% confidence interval for the decline in FVC at 24 weeks exclude the value 120 mL, a value considered to represent the natural course decline in 24 weeks for an untreated subject. The total of 60 subjects will be included to compensate non-evaluable subjects for reasons such as early drop out.

Analysis Data Sets

The full analysis set (FAS) will consist of all subjects who have received at least one dose of IMP and who has at least one post-baseline assessment of efficacy.

The per protocol analysis set (PPAS) will be a subset of FAS and consist of all subjects without any major protocol deviations that are judged to compromise the analysis of the data and with data collection up to at least week 24. All protocol deviations will be judged as major or minor prior to database lock.

The safety analysis set (SAS) will consist of all subjects who have received at least one dose of IMP.

The pharmacokinetic (PK) dataset will consist of all subjects selected for PK assessments and with at least one post-dose plasma sample analysed.

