3.7 Rationale for Trial Design

Given the urgent need for effective medicines in IPF, proof of concept for C21 is sought within this open-label, single-arm, multi-centre trial evaluating the safety, efficacy, and pharmacokinetics of subjects with IPF.

Since this is the first trial where patients are administered repeated doses of C21, the primary objective of the trial will be to evaluate the safety (including tolerability) of C21 in an IPF population.

Clinical Trial Protocol

Vicore Pharma AB
Trial ID: VP-C21-005

Version: 7.0
Date: 15-Sep-2021

The expected average FVC reduction in untreated IPF patients is 120 mL/24 weeks (Richeldi et al., 2014), with the same rate of decline independent of disease severity (Kolb et al., 2017) (see also Section 13.3). The consistent information on the natural course of the disease supports an open-label single-arm design. Since the individual rate of decline in lung function (FVC) is not constant, a minimum duration of IMP exposure of 24 weeks is considered necessary to investigate the efficacy of C21, with respect to demonstrating a significantly lower rate of decline in FVC than expected for this population, and durability of this response. Thus, extended treatment up to a maximum of 36 weeks may be offered as long as it is considered safe by the investigator to continue treatment, on an individual patient level.

A sample size of 60 subjects is considered sufficient for an initial investigation of safety and efficacy, whilst preventing unnecessary exposure of subjects to trial drug (see rationale for sample size regarding efficacy in Section 13.1).

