5.2 Exclusion Criteria

- 1) Previous use of antifibrotic treatment for an interstitial lung disease (e.g. nintedanib or pirfenidone) for >6 months
- 2) Smoking (including e-cigarettes) within 6 months prior to Visit 1
- 3) Body mass index (BMI) >35 or <18
- 4) IPF exacerbation within 3 months prior to Visit 1, as defined by [Collard et al. \(2016\)](#):
 - Acute worsening or development of dyspnoea typically <1 month duration
 - Computed tomography with new bilateral ground-glass opacity and/or consolidation superimposed on a background pattern consistent with usual interstitial pneumonia pattern (if no previous computed tomography is available, the qualifier “new” can be dropped)
 - Deterioration not fully explained by cardiac failure or fluid overload
- 5) Concurrent serious medical condition with special attention to cardiac or ophthalmic conditions (e.g. contraindications to cataract surgery), or moderate to severe hepatic impairment, which in the opinion of the investigator makes the subject inappropriate for this trial
- 6) Malignancy within the past 5 years with the exception of *in situ* removal of basal cell carcinoma and cervical intraepithelial neoplasia grade I
- 7) Treatment with any of the medications listed below within 4 weeks prior to Visit 1:
 - Strong CYP3A4 inducers (e.g. rifampicin, phenytoin, St. John’s Wort)
 - Strong CYP3A4 inhibitors (e.g. clarithromycin, ketoconazole, nefazodone, itraconazole, ritonavir)
 - Medicines that are substrates of CYP1A2, CYP3A4 or CYP2C9 with a narrow therapeutic range
 - Experimental drugs
 - Antifibrotic treatment
 - Any systemic immunosuppressive therapies other than:
 - Inhaled corticosteroids which can be used throughout the trial period provided the dose is kept stable
 - Corticosteroids for the treatment of acute exacerbations
 - The continuation of a stable daily dose of ≤ 15 mg prednisolone, or equivalent
- 8) Treatment with any of the medications listed below within 2 weeks prior to Visit 1:
 - Proton pump inhibitors (PPIs) more than once daily
 - Histamine H2 receptor antagonists (H2RAs)
 - Sulphasalazine and rosuvastatin

Clinical Trial Protocol

Vicore Pharma AB
Trial ID: VP-C21-005

Version: 7.0
Date: 15-Sep-2021

- High dose breast cancer resistance protein sensitive substrates (other than sulphasalazine or rosuvastatin)

9) Any of the following findings at Visit 1:

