- Prolonged QTcF (QT interval with Fridericia's correction) (>450 ms), clinically significant cardiac arrhythmias or any other clinically significant abnormalities in the resting ECG, as judged by the investigator
- Increased AST or ALT >3 times Upper Limit of Normal (ULN), or bilirubin >1.5 times ULN
- Positive results for hepatitis B surface antigen (HBsAg), hepatitis C virus antibody (HCVAb) or human immunodeficiency virus 1+2 antigen/antibody (HIV 1+2 Ag/Ab)
- Positive serum pregnancy test (minimum sensitivity 25 IU/L or equivalent units of human chorionic gonadotropin [HCG])

10) Inability to generate lung function data at Visit 1 meeting the minimum standards of the ATS/ERS 2005 guideline ([Miller et al. 2005](#)), as determined by central review

11) Clinically significant abnormal laboratory value at Visit 1 indicating a potential risk for the subject if enrolled in the trial as evaluated by the investigator

12) Pregnant or breast-feeding female subjects

13) Female subjects of childbearing potential not willing to use contraceptive methods as described in Section [5.3.1](#)

14) Male subjects not willing to use contraceptive methods as described in Section [5.3.1](#)

15) Subjects not willing to adhere to dietary restrictions during the trial period as described in Section [5.4](#)

16) Participation in any other interventional trial during the trial period

17) Subjects known or suspected of not being able to comply with this trial protocol (e.g. due to alcoholism, drug dependency or psychological disorder)

18) Discontinuation or change of previous antifibrotic treatment (e.g. nintedanib or pirfenidone) due to disease progression

Clinical Trial Protocol

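### Excluding 120 mL carries the implied 5% error against the untreated course only if untreated subjects here would lose at least 120 mL, and the plan gives that benchmark no uncertainty

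*Combined protocol and SAP*

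**What the plan says.** Section 13.1 bases the sample size on "assumptions of a 40 mL decline in FVC/24 weeks and a standard deviation of 200 mL". With 55 evaluable subjects it claims 90% power for the 90% confidence interval of the 24-week decline to exclude 120 mL, "a value considered to represent the natural course decline in 24 weeks for an untreated subject". Sixty subjects are included to allow for non-evaluable ones.

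Section 3.7 gives the origin of the benchmark: "The expected average FVC reduction in untreated IPF patients is 120 mL/24 weeks", from one cited trial and, on the strength of a second cited source, "with the same rate of decline independent of disease severity". It then argues that "The consistent information on the natural course of the disease supports an open-label single-arm design", and describes the aim as "demonstrating a significantly lower rate of decline in FVC than expected for this population". No standard error, interval or range accompanies the 120 mL in either section.

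Section 13.3.1 plans the mean change at weeks 12, 24 and 36 with two-sided 90% intervals, and a mixed model as a secondary approach. Section 13.3.4.1 imputes missing week-24 values at the same rate (60 mL per 12 weeks). The alternate imputations in section 13.3.4.2 concern missing data from COVID-19. No section varies the reference value. FVC change is a secondary endpoint (4.5); the primary endpoint is adverse events (4.4). Section 13 announces a separate, more detailed SAP, which is not part of the available document.

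**The concern.** There is no control arm, so the comparison with 120 mL is the only one that can turn the observed decline into evidence of benefit. The interval reflects the sampling error of this trial alone. Two other uncertainties are left out: the sampling error of the external average, and any difference between its source population and the subjects enrolled here.

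Section 3.7 is about the untreated course in this population, whereas section 13.1 computes the chance of excluding a fixed number. The two agree only to the extent that 120 mL is the untreated decline here. If that decline is smaller, an inert drug can meet the criterion more often than the 90% interval suggests. Section 3.7 seeks proof of concept and section 3.6 says the data will guide further trials, so such a result would carry weight.

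**Working it through.** **Inputs from section 13.1:** n = 55, decline on C21 40 mL, SD 200 mL, benchmark 120 mL, two-sided 90% interval. The 5% one-sided error is implied by that interval and is not stated as a number.

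**1. The plan's own figure.** SE = 200/√55 = 26.97 mL; difference = 120 − 40 = 80 mL.
- Normal approximation: Φ(80/26.97 − 1.645) = Φ(1.321) = 90.7%; n needed for 90% power is 54.
- Noncentral t, 54 df, noncentrality 80/26.97 = 2.97: power 90.05%; n needed is 55.

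The stated 90% with 55 subjects is reproduced, with 120 mL entered at zero variance.

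**2. What excluding 120 mL requires.** With an observed SD of 200 mL, the interval lies below 120 mL when the mean decline is under about 75 mL (t-based cut-off 74.9 mL).

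**3. Inert drug, true untreated decline u (assumed range).** The mean decline is then centred on u. The chance of excluding 120 mL is the upper tail of a noncentral t (54 df, noncentrality (120 − u)/26.97) beyond its one-sided 5% critical value. The last column is a different quantity: the power to exclude u itself when the decline on C21 is 40 mL, from noncentrality (u − 40)/26.97.

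| u (mL/24 weeks) | Inert drug: chance of excluding 120 mL | C21 decline 40 mL: power to exclude u |
|---|---|---|
| 140 | 0.9% | 98% |
| 130 | 2.2% | 95% |
| 120 | 5.0% | 90% |
| 110 | 10.1% | 82% |
| 100 | 18.1% | 71% |
| 90 | 29.2% | 57% |

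The error is at most 5% for u of 120 mL or more and rises quickly below that. The probability of excluding the number 120 when C21 subjects lose 40 mL stays at 90% in every row, because u does not enter it.

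**4. Sampling error of the benchmark.** Suppose 120 mL is an unbiased estimate with standard error s (assumed). Treating it as exact gives an average one-sided error of Φ(−1.645 × 26.97/√(26.97² + s²)). Carrying s in the comparison gives power Φ(80/√(26.97² + s²) − 1.645). Both use the normal approximation with n = 55.

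| s (mL) | √(26.97² + s²) | Average error if 120 mL is treated as exact | Power if s is carried |
|---|---|---|---|
| 5 | 27.43 | 5.3% | 90% |
| 10 | 28.76 | 6.2% | 87% |
| 15 | 30.86 | 7.5% | 83% |

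Over these assumed ranges, a shift in the population matters more than the benchmark's sampling error: a 20 mL shortfall more than triples the error, while s = 10 mL adds about one percentage point.

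**The case against.** The strongest reply is that section 13.1 is correct as written. It gives the probability of excluding a number, states no alpha or success rule, and presents 120 mL openly as an assumption. Section 13.3.1 plans estimation with intervals for a secondary endpoint in an early trial, and dependence on an external reference comes with any single-arm design. The arithmetic does stand, and the 5% is inferred. But section 3.7 speaks of a significantly lower decline than expected in this population, so the interval will be read as a test against the untreated course.

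Three stronger readings are tempting and are not supported.
- *The error and power hold only if the untreated decline is exactly 120 mL.* The error is at most 5% at any untreated decline of 120 mL or more, and the stated power does not depend on the untreated decline at all.
- *The entry criteria are shown to remove fast decliners.* Section 5.2 excludes "IPF exacerbation within 3 months prior to Visit 1" and "Discontinuation or change of previous antifibrotic treatment (e.g. nintedanib or pirfenidone) due to disease progression". Either might lower the mean decline, but what matters is the contrast with the cited trial's population. That trial may have applied similar exclusions, and the documents do not say. The second criterion bears only on previously treated subjects. No direction of bias is established.
- *Nothing planned would reveal the problem.* Whether 110, 100 or 90 mL is excluded can be read from the planned interval. What is missing is a commitment to report and interpret it that way, and any allowance for the benchmark's own error.

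The separate SAP may also address this, so its absence from section 13 does not prove that it is unplanned.

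**Conclusion.** The point holds in a limited form. The power statement is right for excluding 120 mL. The implied 5% error transfers to the aim in section 3.7 only if untreated subjects here would lose at least 120 mL, which the documents assume and do not establish. The exposure runs one way: with an inert drug the chance of excluding 120 mL is 10%, 18% or 29% if the untreated decline is 110, 100 or 90 mL, against 2% if it is 130 mL. A benchmark standard error of 5 to 15 mL moves the average error from 5% to between 5.3% and 7.5%.

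These figures rest on n = 55, SD 200 mL and normally distributed changes, and ignore the effect of imputed values. The untreated declines and benchmark standard errors are assumed, because the documents give neither. The point is a gap in how the comparison is qualified, and it does not call for a different sample size or reference value.

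**What to change.** Keep 120 mL and the sample size.

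1. In the SAP, pre-specify as a sensitivity analysis an interval for the difference from the benchmark: (120 − observed mean decline) ± 1.645 × √(SE² + s²), where SE is the trial's standard error and s the benchmark's. Take or derive s from the cited source. If none is available, use a stated range such as 5, 10 and 15 mL.
2. Report the week-24 result against benchmarks on both sides of 120 mL, for example 90 to 140 mL, and word any efficacy conclusion by the range of untreated declines that the interval excludes.
3. In section 13.1, say that the 90% power is for excluding 120 mL and not for beating the true untreated decline.

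The cost is SAP wording, one extra interval and one table. The stated operating characteristics become slightly less favourable: with 55 subjects, power of about 90%, 87% or 83% at an assumed benchmark standard error of 5, 10 or 15 mL.

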5.6 Withdrawal Criteria

5.6.1 Evaluation for Withdrawal after each 12 Week Treatment Period

After completion of each 12-week treatment period, the investigator will make a medical evaluation and decide if the subject may continue into the next 12-week treatment period. The decision will be based on:

- No immediate need for other antifibrotics
- A positive risk/benefit balance

Clinical Trial Protocol

Vicore Pharma AB
Trial ID: VP-C21-005

Version: 7.0
Date: 15-Sep-2021

Failure to pass the medical evaluation will result in the subject being withdrawn from the trial (see Section 5.4.2).

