5.7 Withdrawal from Trial

A subject will be withdrawn from trial if any of the following occurs:

- A decline from baseline in FVC value of > 10% predicted on 2 consecutive occasions and an FVC <60% predicted (*Specific for UK*: FVC <80 % predicted ; or FVC <60% predicted for subjects previously treated with nintedanib and/or pirfenidone, or refused such treatments)
- A decline from baseline in FVC value of 5-10% predicted on 2 consecutive occasions and worsening of respiratory symptoms and FVC <60% predicted (*Specific for UK*: FVC <80 % predicted; or FVC <60% predicted for subjects previously treated with nintedanib and/or pirfenidone, or refused such treatments)
- Consistent failure to comply with dietary requirements in Section 5.4, according to the investigators
- The investigator judges it necessary due to medical reasons
- Failure to pass the medical evaluation after each 12-week treatment period (see Section 5.6.1)
- It is the wish of the subject to withdraw for any reason
- Pregnancy

An end-of-trial visit (Visit 15) must be completed for all subjects withdrawn from the trial.

Subjects withdrawn due to pregnancy will be followed – as consented to – until termination or delivery and the infant must be followed at least until the age of one month.

Subject who withdraws prior to week 12 will be replaced until 60 subjects have completed the 12-week visit.

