13.3 Efficacy Analysis

13.3.1 Efficacy Endpoint Analysis

The change in FVC from baseline to week 12, 24, and 36 will be calculated for each subject and summarised using the population mean and corresponding 90% two-sided confidence intervals. For early withdrawn subjects, the value representing week 24 will be calculated assuming a decline rate of 60 mL/12 weeks for the period between last visit and week 24.

As a secondary approach, a mixed model will be fitted to the FVC data collected from each time point within a subject up to week 36 or last visit if withdrawn earlier. A linear or piece-wise linear relation for the FVC decline using one or several slopes will be used to model the data depending on the actual curve shape. Model parameters will be summarised. Model will be used to assess the

Clinical Trial Protocol

Vicore Pharma AB
Trial ID: VP-C21-005

Version: 7.0
Date: 15-Sep-2021

average decline in FVC after 12, 24, and 36 weeks of treatment together with 90% two-sided confidence intervals.

The number of rapid decliners in FVC, fulfilling the withdrawal criteria during the trial, will be summarised.

FVC and FEV1 will further be summarised by visit using descriptive statistics and visualised using mean value plots (with imputation). For FVC, further a plot of the model fit, that is observed means versus the model predicted curve, will be constructed.

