13.3.4 Statistical/Analytical Issues

13.3.4.1 Missing Data

To summarise the change in FVC from baseline to week 24, missing data at week 24 will be imputed assuming a decline rate of 60 mL/12 weeks for the period between last visit and week 24. No imputation will be done for the mixed model or for the safety summaries.

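### Does requiring data to week 24 for the per-protocol set bias the FVC comparison with 120 mL?

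*Combined protocol and SAP*

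**What the plan says.** Section 13.1 gives the full analysis set (FAS) no duration condition: one dose and one post-baseline efficacy assessment are enough. The PPAS is the part of the FAS free of major deviations and "with data collection up to at least week 24". On sample size, the same section states: "The total of 60 subjects will be included to compensate non-evaluable subjects for reasons such as early drop out".

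Section 5.7 requires withdrawal for "A decline from baseline in FVC value of > 10% predicted on 2 consecutive occasions and an FVC <60% predicted", with a UK-specific floor of 80% for some subjects. A second rule covers a smaller decline with worse respiratory symptoms and the same floor. Failing the evaluation at the end of a 12-week period also means withdrawal; one condition for passing is "No immediate need for other antifibrotics" (Section 5.6.1). After withdrawal only Visit 15 remains, 2 to 4 weeks after the last dose (Section 6.1).

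For the week-24 summary, Section 13.3.1 states: "For early withdrawn subjects, the value representing week 24 will be calculated assuming a decline rate of 60 mL/12 weeks". Section 13.3.4.1 repeats that "missing data at week 24 will be imputed assuming a decline rate of 60 mL/12 weeks". The mixed model takes data from "each time point within a subject up to week 36 or last visit if withdrawn earlier". A further line reads: "The number of rapid decliners in FVC, fulfilling the withdrawal criteria during the trial, will be summarised". Section 13.3 does not name the analysis set for any of these. The opening of Section 13 leaves technical detail to a separate statistical analysis plan, to be signed before database lock.

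**The concern.** Membership of the PPAS depends partly on the outcome being estimated. A subject withdrawn at week 12 under the FVC rules has obeyed the protocol, yet cannot be in the per-protocol set. The subjects lost this way are mostly fast decliners, so the mean of those who remain looks better.

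In a randomised trial some of this selection might cancel between arms. Here the mean is set against a fixed 120 mL, so nothing cancels. The imputation for early leavers would also have almost nobody to act on inside the PPAS. Because Section 13.3 names no set, and Section 13.1 counts early drop-outs as non-evaluable when sizing the trial, a reader could think the 120 mL comparison was meant for the PPAS. An inactive drug would then have more than the intended 5% chance of appearing to slow decline.

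**Working it through.** **1. The plan's own figure.** Inputs from Section 13.1: assumed decline 40 mL, reference 120 mL (gap 80 mL), SD 200 mL, two-sided 90% interval, 55 evaluable subjects.

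- Standard error = 200/√55 = 26.97 mL.
- Normal approximation: Φ(80/26.97 − 1.645) = Φ(1.32) = 90.7%.
- Noncentral t: 90.05%.

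The stated 90% power is reproduced.

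**2. Hand check of the shift.** Suppose one of 60 subjects, with an assumed decline of 350 mL, leaves the set while the true mean decline is 120 mL.

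- Shift = (350 − 120)/59 = 3.9 mL.
- Error = Φ(3.9/(200/√59) − 1.645) = Φ(−1.495) = 6.7%, against 5%.

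**3. Simulation of the withdrawal rules.** The visit schedule, the 60% floor, the 200 mL SD and the 120 and 40 mL means come from the documents. Assumed, because the documents do not give them: predicted FVC 3.5 L, baseline normal(80, 12)% predicted truncated at 60%, measurement error 75 mL, 25% with worse symptoms, linear individual declines, and no other drop-out or deviations. An error is counted when the lower 90% limit for mean change lies above −120 mL.

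| True decline 120 mL, N = 60 | Mean change | One-sided error |
|---|---|---|
| Full data, nobody withdrawn | −120.1 mL | 5.0% |
| All subjects, planned imputation | −120.0 mL | 5.0% |
| All subjects, mixed model | −120.0 mL | 5.2% |
| PPAS, week-24 summary | −115.3 mL | 7.1% |
| PPAS, mixed model | −115.2 mL | 7.3% |

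On average 0.9 of 60 subjects leave, and in about 39% of trials nobody does. The 4.8 mL shift is under a fifth of the standard error (200/√60 = 25.8 mL).

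**4. Range of the PPAS shift, true decline 120 mL.**

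- Baseline 90% predicted, no worse symptoms: 1.0 mL, error 5.4%.
- Baseline 72%, half with worse symptoms: 12.4 mL, 12.3%.
- Visit 15 spirometry counted for those withdrawn at week 21 (it falls at weeks 23 to 25): 2.8 mL, 6.2%.
- Week-12 evaluation also removing 25% or 50% of subjects down at least 5% predicted at weeks 9 and 12: about 10 or 16 mL, 10.7% or 15.3%. All subjects with imputation: −118.8 or −117.6 mL, 5.5% or 6.0%.
- A second set of assumptions (predicted FVC 3.7 L, slope SD 150 mL per 24 weeks, measurement SD 94 mL, baseline mean 75 to 85%): about 2 to 15 mL with the 60% floor, and 8 to 29 mL if every subject fell under the UK 80% floor.

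**5. Upper bound.** If the fraction f removed were exactly the worst decliners, shift = 200·φ(z_f)/(1 − f). For f = 5/60 = 8.3%, the plan's own allowance, this is 33.4 mL, or 42% of the 80 mL gap. The withdrawal rules do not select that sharply.

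**6. Under the plan's assumed 40 mL decline.** The central shift is 2.4 mL, and the chance of excluding 120 mL is 93.5% in the PPAS against 91.8% for all subjects with imputation.

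**7. Which set the text implies.** In a set that demands data to week 24, a rule for subjects withdrawn before week 24 would be nearly empty, and a model clause about the last visit of early leavers would apply only to departures between weeks 24 and 36. Both provisions make full sense only in the wider set. That is the set in which step 3 shows the error at or near its nominal level.

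**The case for a change.** The best argument for acting is that the text does not exclude a PPAS reading, the direction of the bias is known, and the repair costs one clause and one sentence. It would keep protocol-directed withdrawals in the PPAS with week 24 imputed, and name the FAS for the 120 mL comparison. The bias also cannot be called slight in general: the documents give neither the share withdrawn for decline nor the share of UK subjects, and replacing those who leave before week 12 does not remove the selection (4.7 mL and 7.0% in the central case).

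The mechanism, the direction and the uncertainty about size all stand. The need for a change does not. Treating early drop-outs as non-evaluable is a margin for sizing and does not define the analysis set. Redefining the PPAS would bring it close to the FAS and weaken it as a contrasting set. It would also leave some of the selection in place, since subjects withdrawn on the investigator's medical judgement (Section 5.7) or to receive a different treatment (Section 3.9) would still be excluded. Section 3.7 regards 24 weeks of exposure as the minimum for judging efficacy, which is a fair reason to have a set built on that exposure. Whether it is called per-protocol or completers is a matter of labelling.

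**Conclusion.** The concern is right about what the PPAS would do and does not reach any analysis the plan schedules. A week-24 FVC mean computed in the PPAS would tend toward slower decline: 4.8 mL in the central case, and about 1 to 29 mL across the simulated scenarios at a true decline of 120 mL. These figures rest on assumed baseline FVC, measurement error, symptom rates, week-12 removals and UK share.

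The week-24 summary and the mixed model are written for a set that keeps early leavers. Run that way, the summary stayed within 2.5 mL of the full-data mean with error at most 6.0% in the scenarios of steps 3 and 4 where it was evaluated, and the mixed model was on target in the central case. FVC is a secondary endpoint, and rapid decliners are counted separately, so the subjects in question remain visible in the report. The unnamed analysis set is a gap that an analyst following Section 13.3 would fill with the FAS, and the PPAS definition is a defensible trade-off. No planned result would change, so no amendment is warranted.
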